## National Cholesterol Education Program (NCEP) Lipid Categories

 In addition to DAIDS toxicity grades (see protocol), lipid values will be categorized according to the 2001 NCEP Adult Lipid Guidelines [Grundy, 2001]

Parameter	Value Range (mmol/L)	Value Range (mg/dL)	Category
Triglycerides	<1.70	<150	Normal
	1.70 to <2.26	150 to <200	Borderline High
	2.26 to <5.65	200 to <500	High
	≥5.65	≥500	Very High
Total Cholesterol	<5.18	<200	Desirable
	5.18 to <6.21	200 to <240	Borderline High
	≥6.21	≥240	High
HDL Cholesterol	<1.04	<40	Low

Laboratory Parameters			
	1.04 to <1.56	40 to <60	Normal
	≥1.56	≥60	High
LDL Cholesterol	<2.59	<100	Optimal
	2.59 to <3.37	100 to <130	Near/Above Optimal
	3.37 to <4.14	130 to <160	Borderline High
	4.14 to <4.92	160 to <190	High
	≥4.92	≥190	Very High

## **Other Safety Endpoints**

### **Corrected QTC**

When not entered directly in the eCRF, corrected QT intervals by Bazett's (QTcB) and Fridericia's (QTcF) formulas will be calculated, in msec, depending on the availability of other measurements.

If RR interval (in msec) is provided then missing QTcB and/or QTcF will be derived as

$$QTcB = \frac{QT}{\sqrt{RR/1000}} \qquad \qquad QTcF = \frac{QT}{\sqrt[3]{RR/1000}}$$

where uncorrected QT interval is also measured in msec.

If RR interval is not provided directly and one of QTcB or QTcF has been entered, then RR interval can be obtained from the above formulas and used to calculate the other correction method value; i.e.,

$$QTcB = \sqrt{\frac{QTcF^3}{QT}}$$

$$QTcF = \sqrt[3]{QT \cdot QTcB^2}$$

### 12.6.5. Health Outcomes

## HIVTSQs

## Questionnaire (Questions 1-12 are scored 0-6)

CCI - This section contained Clinical Outcome Assessment data collection questionnaires or indices, which are protected by third party copyright laws and therefore have been excluded.

#### **Treatment Satisfaction Score**

- Total Treatment Satisfaction Score is computed with items

  CCI
- Item 12 will not be included in Total Treatment Satisfaction Score. Instead, it will be treated as a stand-alone item only.
- Higher scores represent greater treatment satisfaction as compared to the past few weeks.
- A maximum of 5 items can be missing, which can be imputed to reflect the mean of the completed item scores. If 6 or more items are missing, then the treatment satisfaction scale score should not be computed and would remain missing.

### **Individual Item Scores**

- Items are rated as (CCI), etc.).
- Higher scores represent greater satisfaction with each aspect of treatment
- For individual item scores outputs, missing scores will not be computed (according to Page 7 of the [HIVDQoL User Guidelines, 2018]) and would remain missing.

#### **HIVTSQc**

## Questionnaire (Questions 1-12 are scored -3 to 3)

CCI - This section contained Clinical Outcome Assessment data collection questionnaires or indices, which are protected by third party copyright laws and therefore have been excluded.

## **Treatment Satisfaction Score (change)**

- Total Treatment Satisfaction Score is computed with items
- Item 12 will be computed as an individual item only.
- The higher the score, the greater the improvement in satisfaction with treatment; the lower the score, the greater the deterioration in satisfaction with treatment. A score of 0 represents no change.
- A maximum of 5 items can be missing, the missing scores will be imputed with the mean of the
  completed item scores. If 6 or more items are missing, then the overall treatment satisfaction
  scale score should not be computed and will remain missing.

## **Individual Treatment Change Item Scores**

- Items are rated as ccl etc.) to ccl , etc.).
- The higher the score, the greater the improvement in satisfaction with each aspect of treatment and the lower the score, the greater the deterioration in satisfaction with each aspect of treatment.

#### **HIVDQoL**

## Questionnaire (Questions I and II are overview items and 1-26 are domain-specific items)

This questionnaire has been provided in three different languages: English (US and Canadian), French (Canadian), Spanish (US). Below is an example of the questionnaire.

third party copyright laws and therefore have been excluded.

CCI - This section contained Clinical Outcome Assessment data collection questionnaires or indices, which are protected by third party copyright laws and therefore have been excluded.
third party copyright laws and therefore have been excluded.

CCI - This section contained Clinical Outcome Assessment data collection questionnaires or indices, which are protected by third party copyright laws and therefore have been excluded.
umu party copyright laws and merelore have been excluded.

CCI - This section contained Clinical Outcom third party copyright laws and therefore have	ne Assessment data colle	ection questionnaires or ind	lices, which are protected by
and party copyright laws and therefore have	been excluded.		

CCI - This section contained Clinical Outcome Assessment dathird party copyright laws and therefore have been excluded.	ata collection questionnaires or indices, which are protected by
unitu party copyright laws and therefore have been excluded.	

CCI - This section contained Clinical Outcome Assessment da	ata collection questionnaires or indices, which are protected by
third party copyright laws and therefore have been excluded.	

CCI - This section contained Clinical Outcome Assessment data third party copyright laws and therefore have been excluded.	collection questionnaires or indices, which are protected by
unitu party copyright laws and therefore have been excluded.	

CCI - This section contained Clinical Outcome Assessment data collection questionnaires or indices, which party copyright laws and therefore have been excluded.	n are protected by third
party copyright laws and therefore have been excluded.	

CCI - This section contained Clinical Outcome Assessment dathird party copyright laws and therefore have been excluded.	nta collection questionr	naires or indices, whic	ch are protected by
third party copyright laws and therefore have been excluded.			

CCI - This section contained Clinical Outcome Assessment data collection questionnaires or indices, which are protected by hird party copyright laws and therefore have been excluded.
thru party supprignations and therefore have been excluded.
Individual Domain Items [HIVDQoL User Guidelines, 2018]
There are two overview items which are rated as:
There are two overview items which are rated as.     : GCI
o II: CCI
CCI - This section contained Clinical Outcome Assessment data collection questionnaires or indices, which
are protected by third party copyright laws and therefore have been excluded.
• The 26 domain-specific items include two rating scales, one measuring impact, part a, and the
other measuring the importance of the domain for QoL, part b.
The impact scores are rated as CCI  to CCI  to CCI  The impact scores are rated as CCI  The impac
and the importance scores are rated as column to column to
W. I.
Weighted Impact Scores [HIVDQoL User Guidelines, 2018]
The impact ratings are multiplied by the corresponding importance rating to provide a
weighted-impact score for each applicable domain from CCI to CCI

CCI

- If one part of a domain response (i.e. either part a or part b) is missing, a weighted impact score cannot be imputed for that question.
- If more than one option has been selected for a question, then if the options are consecutive (e.g. 2 and 3), then take the mid-point (i.e. 2.5) to be the final score for that question. However, if the two answers are not immediately next to each other (e.g., 0 and 3), treat the score as missing.

## Average Weighted Impact (AWI) Score [HIVDQoL User Guidelines, 2018]

- Weighted impact scores are summed and divided by the number of applicable domains (excluding domains with missing data), to give an overall AWI score. The non-applicable domains are hence ignored.
- If there are more than three items with missing scores out of the 14 core domain-specific items which do not have the N/A option, then the AWI score will not be computed.
- Item 23 and item 25 are not included when calculating AWI scores along with the two overview items I and II.

#### **Reason for Switch**

#### Questionnaire

You have chosen to continue participating in a clinical study where your daily oral HIV medication will be switched to a Long-Acting injectable HIV medication.

CCI

[select all that apply]:

CCI - This section contained Clinical Outcome Assessment data collection questionnaires or indices, which are protected by third party copyright laws and therefore have been excluded.

[figure not shown]
### **Data handling**

- If the questionnaire is taken beyond ± 2 weeks window from maintenance phase treatment start date (i.e. Study Day < -14 or Study Day > 14) it will be considered not evaluable and will not be included in the summary.
- Any missing values will remain missing (i.e. no imputation).

#### Preference question

#### Questionnaire

CCI - This section contained Clinical Outcome Assessment data collection questionnaires or indices, which are protected by third party copyright laws and therefore have been excluded.

## **12.6.6.** Virology

## Genotype

## **Amino Acid Changes**

- A mutation is considered present whenever the encoded amino acid residue differs from the amino acid that would have been encoded by the wild-type (e.g., HXB2, NL43) comparator gene; e.g., Q148K.
- If the encoded amino acid is seen as a mixture of wild-type and mutant amino acid, e.g., Q148Q/K, the mutated amino acid is considered present at the codon of interest.
- If the encoded amino acid is seen as a mixture of two or more amino acids, which may or may
  not include wild type, e.g., Q184K/H or Q184K/H/Q, etc., for the purposes of calculating the
  number of mutated amino acids, only one mutation is considered to be present at the codon of
  interest.

## **Representation of Amino Acid Changes**

Mutations	Amino acid change	
T69S	Single mutation from amino acid 'T' (vendor reference) to 'S' (sample) at codon '69'	
Q148H/K/R	Mixture of amino acid mutations 'H', 'K' and 'R' (sample) from amino acid 'Q'	
	(vendor reference) at codon '148'	
_69_1T	First insertion of amino acid 'T' (sample) at codon '69'	
_69_2S	Second insertion of amino acid 'S' (sample) at codon '69'	
_69_3S/A	Third insertion of a mixture of amino acids 'S' and 'A' (sample) at codon '69'	
L74L/-	Mixture of amino acid 'L' (sample) and a deletion at codon '74'	
V75-	Single deletion of amino acid (sample) at codon '75'	

#### **Resistance Associated Mutations**

• Known INI mutations associated with the development of resistance to BIC, RAL, EVG or DTG:

Amino Acids in	H51Y, T66A/I/K , E92Q/V /G, Q95K, T97A, G118R, F121Y , E138A/K/T,
HIV Integrase for	G140A/C/R/S**, Y143C/H/R/K/S/G/A, P145S, Q146P, S147G,
Analysis	Q148H/K/R/N , V151 A/I/ L , S153F/Y, N155H/ S/T, E157Q, G163R/K,
	S230R, D232N, R263K, L68V/I*, L74I/M*, E138D*, V151I*, G193E*

#### NOTES:

Draft listing; may be modified in case of additional substantive data availability.

INI mutations listed taken from Stanford HIV Resistance Database (http://hivdb.stanford.edu/DR/cgi-bin/rules\_scores\_hivdb.cgi?class=INI cited 25Oct2019) and accessed on 28Jan2020.

INI substitutions listed above in bold had a score of =60.

 Major resistance mutations to other classes (i.e., NRTI, NNRTI, PI) as defined by the International Antiviral Society-USA (IAS-USA). The most up to date IAS-USA guidelines available at the time of DBF will be used in the analysis [Wensing, 2019].

Class	Mutations
NRTIs	M41L, A62V, K65R/E/N, D67N, 69 insert, K70E/R, L74V, V75I, F77L, Y115F, F116Y, Q151M, M184V/I, L210W, T215Y/F, K219Q/E
NNRTIs	L100I, K101E/P, K103N/S, V106A/M, V108I, E138/A/G/K/Q/R, V179L,Y181C/I/V, Y188C/L/H, G190S/A, H221Y, P225H, F227C, M230I/L,
Pls	D30N, V32I , M46I/L, I47A/V, G48V, I50V/L, I54M/L/V, Q58E, T74P, L76V, V82A/T/F/L/S, N83D, I84V, N88S, L90M

Note: List generated from IAS\_USA Guideline, [Wensing, 2019]

#### **Phenotype**

#### Phenotypic Susceptibility

Phenotypic susceptibility to all licensed antiretroviral drugs and CAB will be determined using PhenoSense HIV assays from Monogram Inc. and will be reported as fold change (FC) in IC50 relative to wild-type control virus NL4-3, i.e., FC of sample virus = IC50 of sample virus/IC50 of control virus.

Phenotypic susceptibilities will be categorised according to FC as shown in the tables below (based on Monogram PhenoSense assay). Clinical cutoffs (where available) or biological cutoffs by PhenoSense will be used to define the phenotypic susceptibility of background treatment by Monogram.

Replication capacity is generated as part of standard phenotypic assays

\* Denotes additional INI mutations added as they were identified during in vitro passage of DTG or seen in a previous DTG study in INI-experienced subjects (ING112574).

\*\*G140R is potentially associated with CAB based on in-stream data monitoring of CVF participants

PhenoSense Algorithm			
Drug	Abbreviation	Class	PhenoSense cutoff
Abacavir	ABC	NRTI	$(4.5 - 6.5)^a$
Lamivudine	3TC	NRTI	3.5 a
Didanosine	ddl	NRTI	(1.3 – 2.2) a
Stavudine	d4T	NRTI	1.7 a
Zidovudine	AZT (ZDV)	NRTI	1.9
Emtricitabine	FTC	NRTI	3.5
Tenofovir	TDF (TAF)	NRTI	(1.4 – 4) a
Delavirdine	DLV	NNRTI	6.2
Efavirenz	EFV	NNRTI	3
Nevirapine	NVP	NNRTI	4.5
Etravirine	ETR	NNRTI	(2.9-10) a
Rilpivirine	RPV	NNRTI	2.0
Fosamprenavir/r	FPV/r	PI	(4-11) a
Atazanavir	ATV	PI	2.2a
Atazanavir/r	ATV/r	PI	5.2 a
Indinavir/r	IDV/r	PI	10 a
Lopinavir/r	LPV/r	PI	(9 – 55) a
Nelfinavir	NFV	PI	3.6
Saquinavir/r	SQV/r	PI	(2.3 – 12) a
Tipranavir/r	TPV/r	PI	(2 – 8) a
Darunavir/r	DRV/r	PI	(10 – 90) a
Ritonavir	RTV	PI	2.5
Enfuvirtide	T20	FI	6.48
Cabotegravir	CAB	INI	2.5
Raltegravir	RAL	INI	1.5
Elvitegravir	EVG	INI	2.5
Dolutegravir	DTG	INI	(4-13) a
Bictegravir	BIC	INI	(2.5 - 10)

clinical cutoff (lower cutoff - higher cutoff).

Phenotypic susceptibility to each drug in a subject's background regimen is determined by applying drug-associated cutoffs as defined by the PhenoSense algorithm to the phenotypic fold resistance as below:

## **Full Sensitivity**

Fold Change	Interpretation
> clinical lower cutoff or biologic cutoff	resistance
≤ clinical lower cutoff or biologic cutoff	sensitive

## **Partial Sensitivity**

Fold Change	Interpretation
> clinical higher cutoff	resistance
≤ clinical higher cutoff and > clinical lower cutoff	partially sensitive
≤ clinical lower cutoff	sensitive

PHENOTYP dataset from Monogram contains the phenotypic susceptibility for each drug derived from the cutoff listed above. Thus, phenotypic susceptibility (i.e. full sensitivity and partial sensitivity) will not be re-derived for our analysis.

### **Genotypic and Net Assessment Susceptibility**

Genotypic and Net assessment susceptibility to all licensed antiretroviral drugs and CAB will be determined from Monogram Inc. Net assessment susceptibility will be reported with the categories of 'resistance', 'partially sensitive', and 'sensitive' as what will be performed for phenotypic susceptibility. Genotypic and Net assessment susceptibility will be assessed at time of CVF using plasma sample, Genotypic susceptibility may be assessed at baseline using PBMC.

# 12.7. Appendix 7: Reporting Standards for Missing Data

# 12.7.1. Premature Withdrawals

Element	Reporting Detail
General	Subject study completion (i.e. as specified in the protocol) was defined as: Participants are considered to have completed the study if they remain on therapy (i.e., have not permanently discontinued study intervention) and satisfy one of the following:
	Assigned to either treatment group, completed the Maintenance Phase (Month 12 for DTG +RPV participants only), remaining on study until commercial supplies of CAB LA + RPV LA Q2M or DTG + RPV regimens become locally available or development of CAB LA + RPV LA is terminated;
	Additionally, participants will continue this study until:
	the participant no longer derives clinical benefit,
	the participant meets a protocol-defined reason for discontinuation
	Participants who withdraw from CAB LA + RPV LA and go into the LTFU Phase will be considered to have prematurely withdrawn from the study intervention.
	• In addition to the 52-week Follow-Up phase required for participants who receive one or more injections with CAB LA or RPV LA, an in-clinic Follow-Up visit will be conducted approximately 4 weeks after the last dose of study medication for participants who withdraw from the DTG + RPV regimen with ongoing AEs, and serious adverse events (SAEs) and also any laboratory abnormalities that are considered to be AEs or potentially harmful to the participant, at the last on-study visit. Assessments at the Follow-up visit should reflect any ongoing complaints (e.g., blood draws to follow a laboratory abnormality). Follow-Up visits are not required for successful completion of the study.
	Withdrawn participants will not be replaced
	All available data from participants who were withdrawn from the study will be listed and all available planned data will be included in summary tables and figures, unless otherwise specified.
	Withdrawal visits will be slotted as per Appendix 3: Assessment Windows or will be summarised as withdrawal visits.

# 12.7.2. Handling of Missing Data

Element	Reporting Detail
General	
 
Missing data occurs when any requested data is not provided, leading to blank fields on the collection instrument:
 
These data will be indicated by the use of a "blank" in subject listing displays. Unless all data for a specific visit are missing in which case the data is excluded from the table.
 

Element	Reporting Detail
	
 
Answers such as "Not applicable" and "Not evaluable" are not considered to be missing data and should be displayed as such.
 

Outliers	Any participants excluded from the summaries and/or statistical analyses will be documented along with the reason for exclusion in the clinical study report.

# 12.7.2.1. Handling of Missing and Partial Dates

Element	Reporting Detail
General	Partial dates will be displayed as captured in subject listing displays.
Adverse Events	
 
The eCRF allows for the possibility of partial dates (i.e., only month and year) to be recorded for AE start and end dates; that is, the day of the month may be missing. In such a case, the following conventions will be applied for calculating the time to onset and the duration of the event:         
 
Missing Start Day: First of the month will be used unless this is before the start date of study treatment; in this case the study treatment start date will be used and hence the event is considered On-treatment as per Appendix 4: Study Phases and Treatment Emergent Adverse Events.
 
Missing Stop Day: Last day of the month will be used, unless this is after the stop date of study treatment; in this case the study treatment stop date will be used.
 
 
 
Completely missing start or end dates will remain missing, with no imputation applied. Consequently, time to onset and duration of such events will be missing.
 

ART/Non- ART Medications /Medical History	
 
Partial dates recorded in the CRF will be imputed using the following convention:         
 
If the partial date is a start date, a '01' will be used for the day and 'Jan' will be used for the month
 
If the partial date is a stop date, a '28/29/30/31' will be used for the day (dependent on the month and year) and 'Dec' will be used for the month. If medications recorded in the eCRF as prior (e.g. recorded in prior ART or prior ATLAS ART forms, taken prior to study), the earlier date of the imputed and the day prior to the maintenance phase treatment start date will be used, i.e. min (imputed stop date, maintenance phase treatment start date - 1).
 
 
 
For medications with completely missing start date, they will be considered started prior to the maintenance phase treatment start date.
 
For medications with completely missing stop date, they will be considered ongoing unless recorded in eCRF as prior (e.g. recorded in prior ART form, taken prior to study).
 
For ART booster medications, the start and stop dates are not recorded in the database (i.e. missing), the dates will be imputed to be the same as the dates of their parent medications.
 
The recorded partial date will be displayed in listings.
 

Health	For the summary of individual item scores outputs, missing scores will not be
outcomes	computed.

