# Table 16 Days since First Dose of Each Study Phase, Days since Phase Start, AE Duration and Relation to Study Treatment

	Definition	
Days since First Dose (Days) a	AE Start Date – Maintenance Treatment Start Date + 1	
Days since	AE Start Date – Date of Last Dose of Study Treatment prior to/on	
Last Dose	the Start Date of AE + 1	
(Days) a		
Days since	For AEs in Maintenance Phase:	
Phase Start	AE Start Date - Maintenance Treatment Start Date + 1	
	For AEs in Long-term Follow-up Phase:	
	AE Start Date – Date of Last Dose of Study Treatment b	
Duration	AE Resolution Date – AE Start Date + 1	
(Days)		
Drug-related	If relationship is marked 'YES' on Inform/CRF OR value is	
	missing.	

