#### NOTES:

- a. Days since First/Last Dose will only be derived for AEs assigned to maintenance phase and long-term follow-up phase.
- b. Date of Last Dose of Study Treatment = max (Last IM Injection Date, Last Oral Bridging End Date), only applicable to participants who permanently discontinued study treatment.

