## Long-Term Follow Up Study Day

The Long-Term Follow Up (LTFU) Study Day of an event (e.g., lab assessment, start date of AE or HIV associated condition) will be derived as the number of days between the date of the event and the end of IP treatment [i.e max (Last IM Injection Date, Last Oral Bridging End Date)]as follows:

If the onset of event falls in Long-term Follow up phase, then

LTFU Study Day = date of event – end date of IP

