## 12.12.8. Safety Figures

Safety	: Figures				
No.	Population	IDSL / Example Shell	Title	Programming Notes	Deliverable
Advers	se Events				
3.01.	Safety	207966/primar y_02/F3.1	Plot of Common Adverse Events and Relative Risk – Q2M vs. DTG + RPV - Excluding Study Drug ISRs		M12, M26, EOS
Study	Drug Injection	Site Reaction A	dverse Events (display for Q2M arm only)		
3.02.	Safety	207966/primar y_02/F3.2	Plot of Common Study Drug Injection Site Reaction Adverse Events	Only display first panel	M12, M26, EOS
3.03.	Safety	207966/primar y_02/F3.3	Plot of Onset, Duration, and Severity of Overall and Common Study Drug Injection Site Reaction AEs by Maximum Grade - CAB and/or RPV		M12, M26, EOS
3.04.	Safety	207966/primar y_02/F3.4	Plot of Onset, Duration, and Severity of Overall and Common Drug-related Study Drug Injection Site Reaction AEs by Maximum Grade - CAB		M12, M26, EOS
3.05.	Safety	207966/primar y_02/F3.5	Plot of Onset, Duration, and Severity of Overall and Common Drug-related Study Drug Injection Site Reaction AEs by Maximum Grade - RPV		M12, M26, EOS
3.06.	Safety	207966/primar y_02/F3.6	Plot of Incidence of Maintenance Phase Study Drug Injection Site Reaction Adverse Events by Visit (Overall and Common) - CAB and/or RPV		M12, M26, EOS
3.07.	Safety	207966/primar y_02/F3.7	Plot of Incidence of Maintenance Phase Drug-Related Study Drug Injection Site Reaction Adverse Events by Visit (Overall and Common) - CAB		M12, M26, EOS

Safety	: Figures				
No.	Population	IDSL / Example Shell	Title	Programming Notes	Deliverable
3.08.	Safety	207966/primar y_02/F3.8	Plot of Incidence of Maintenance Phase Drug-Related Study Drug Injection Site Reaction Adverse Events by Visit (Overall and Common) - RPV		M12, M26, EOS
3.09.	Safety	207966/primar y_02/F3.9	Plot of Incidence of Grade 3-5 Maintenance Phase Study Drug Injection Site Reaction Adverse Events by Visit (Overall and Common) - CAB and/or RPV		M12, M26, EOS
3.10.	Safety	207966/primar y_02/F3.10	Plot of Incidence of Grade 3-5 Maintenance Phase Drug- related Study Drug Injection Site Reaction Adverse Events by Visit (Overall and Common) - CAB		M12, M26, EOS
3.11.	Safety	207966/primar y_02/F3.11	Plot of Incidence of Grade 3-5 Maintenance Phase Drug- related Study Drug Injection Site Reaction Adverse Events by Visit (Overall and Common) - RPV		M12, M26, EOS
Labora	itory				
3.12.	Safety	207966/primar y_02/F3.12	Scatter Plot of Maximum vs. Baseline for ALT		M12, M26, EOS

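### SAP 12.7.2.1 caps an imputed AE stop day at an undefined treatment stop date with no floor at the AE start, so AEs that begin after treatment get zero or negative durations

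*SAP*

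**What the plan says.** SAP 12.7.2.1 recognises that "The eCRF allows for the possibility of partial dates (i.e., only month and year) to be recorded for AE start and end dates", and gives conventions for calculating time to onset and duration. A missing start day becomes the first of the month, moved up to treatment start if needed. When only the stop day is absent, the convention reads: "Last day of the month will be used, unless this is after the stop date of study treatment; in this case the study treatment stop" (that date then replaces the month end).

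The section does not define the treatment stop date for a long-acting injection. Elsewhere the SAP uses two different ends of treatment:

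- **Last dose.** Table 16 note b has "Date of Last Dose of Study Treatment = max (Last IM Injection Date, Last Oral Bridging End Date"), for participants who permanently discontinued. The Long-Term Follow Up (LTFU) Study Day entry in 12.6.1 likewise takes "the end of IP treatment [i.e max (Last IM Injection Date, Last Oral Bridging End Date")]. Without later oral bridging, both give the last injection date.
- **Last injection + 67 days.** This is used for treatment state (Table 15) and for overall exposure (12.6.2, Extent of Exposure).

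Table 16 defines AE duration as "AE Resolution Date – AE Start Date + 1". SAP 12.12.8 plans Figure 3.03, "Plot of Onset, Duration, and Severity of Overall and Common Study Drug Injection Site Reaction AEs by Maximum Grade", with Figures 3.04 and 3.05 giving the CAB and RPV versions.

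**The concern.** A cap at treatment stop makes sense only if no AE can start or continue after it. Here that is expected by design. Protocol 8.5.1 collects AEs to the final follow-up contact, and the LTFU schedule in Protocol 8.1.3 assesses AEs at every visit for 52 weeks after the last injection. Table 15 still counts 67 days after the last injection as on-treatment. Table 16 derives days since phase start for LTFU AEs, and Listing 26 is dedicated to them.

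The start-day rule pulls a date forward into the treatment period, which is harmless. The stop-day rule pulls a date back to treatment stop, possibly past the event's own start and out of the month the site recorded. The result is impossible durations in the analysis data, and a different convention for stopped and continuing participants.

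**Working it through.** The SAP gives no figure to reproduce, so the rule was applied directly.

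**Inputs.** L = last injection date, with no later bridging. AE start = L + k days. The stop month is recorded and the stop day is missing.

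**Formulas.** Imputed stop = earlier of (end of recorded stop month, cap). Duration = imputed stop - start + 1.

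**Cap = L.** The end of the stop month is never before the AE start, so it is never before L, and the imputed stop is always L. Duration = L - (L + k) + 1 = 1 - k.
- k = 0: 1 day
- k = 1: 0 days
- k = 7: -6 days
- k = 30: -29 days
- k = 90: -89 days

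**Cap = L + 67.** For k up to 67, both candidate dates are on or after the start, so duration is at least 1. From k = 68 the cap precedes the start, and duration = (L + 67) - (L + k) + 1 = 68 - k.
- k = 68: 0 days
- k = 90: -22 days
- k = 200: -132 days

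**DTG + RPV.** With the last oral dose as cap, an AE starting k days later again gets 1 - k.

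**Dated examples**, last injection 10 March 2020, so L + 67 = 16 May 2020. Durations are in days, with the stop day treated as missing:

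| True AE dates | True | Cap L | Cap L + 67 | End of month, no treatment cap |
|---|---|---|---|---|
| 10-16 Mar | 7 | 1 | 22 | 22 |
| 11-16 Mar | 6 | 0 | 21 | 21 |
| 20 Apr-5 May | 16 | -40 | 27 | 42 |
| 20-25 Jun | 6 | -101 | -34 | 11 |

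**Recorded month overridden.** Take a last injection on 1 July and an AE from 5 September with its stop recorded only as October. The recorded month alone implies at least 27 days (5 September to 1 October). Cap L gives a stop of 1 July and 1 - 66 = -65 days. Cap L + 67 gives a stop of 6 September and 2 days. Both contradict the recorded month.

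**Continuing participants.** A Q2M participant still on treatment has no stop date, so the 10 March ISR with stop recorded as March runs to 31 March: 22 days. In a participant who stopped at that injection it is 1 day under cap L, and 22 days under cap L + 67.

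**The case against.** The strongest objection is that the last-injection reading is an inference. The two passages that support it define other terms for other purposes, while the treatment-state and exposure rules add 67 days. A reader might infer that the plan fixes the cap at the last injection and that ISRs at the final injection therefore shrink to one day. The documents do not settle this. Under + 67 days, the -65-day example becomes 2 days and the one-day ISR effect disappears. That part of the objection stands. It does not remove the stop-before-start defect, which only moves to AEs starting from day 68.

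A reader might also infer that only participants who discontinued are affected. That does not follow for DTG + RPV: SAP 12.6.2 gives that arm an IP stop date, and SAP 12.7.1 allows completion at Month 12. The rule therefore reaches completers with an AE starting after the last oral dose.

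Two further points stand. Month-end imputation can overstate short ISRs. Protocol 2.3.1 gives a median ISR duration under one week, and for a true 7-day ISR from 10 March, month end errs by 22 - 7 = 15 days against 7 - 1 = 6 under the last-injection cap. Visible reach is also limited: partial dates are listed as captured, no table or figure title outside ISRs mentions AE duration, and the mock shells are not included in the SAP.

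**Conclusion.** The rule is wrong as written, not merely short of detail. For any AE that starts after the treatment stop date and lacks a stop day, it produces a stop before the start, under either reading of that date and in both arms. The size is 1 - k days if the cap is the last dose, and 68 - k days from day 68 if it is last injection + 67 days.

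The one-day ISR result is conditional. It needs the last-injection reading, onset on the day of the final injection and no later bridging. It would be tempting to add that durations are biased most in people who stopped because of ISRs. The documents give neither the number of such participants nor the frequency of partial stop dates, so that is not established.

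The consequence is confined to AE and ISR duration outputs, chiefly Figures 3.03 to 3.05. Incidence, grade and the primary endpoint do not use the imputed stop day. This is a minor correction, worth making because it is cheap and removes impossible values.

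**What to change.** In SAP 12.7.2.1, impute a missing AE stop day as the end of the recorded month, capped at the date of last study contact or death instead of treatment stop, and never earlier than the AE start date. The cost is one line in that section and the matching change in the ADAE derivation.

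Two smaller repairs are not enough. Flooring the present cap at the AE start removes the negatives but, under the last-injection reading, sets all four dated examples to 1 day. Defining the cap as last injection + 67 days still leaves the June example at -34 days.

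The downside is some overstatement of short ISRs. Continuing participants already carry it, so stopped and continuing participants would then share one convention wherever contact extends past the month end. A footnote on Figures 3.03 to 3.05 with the number of imputed stop days would show how much this matters.
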